11.0 Ketogenic Diet

11.1 Description and approved uses. The ketogenic diet is a high-fat, low-carbohydrate diet that is an established and effective non-pharmacologic treatment for epilepsy in children.²⁸⁻³⁰ A highly restricted Ketogenic diet, or 4:1 ketogenic diet, is often the form of the diet used for recalcitrant seizures and consists of 4 grams of fat to 1 gram of combination of protein and carbohydrate.²⁸⁻³⁰

11.2 Toxicities. The ketogenic diet has been safely used in children and adults for many decades.²⁸⁻³⁰ Patients may experience constipation with use of the ketogenic diet, especially during the initiation phases of the ketogenic diet.²⁸⁻³⁰ Patients should be monitored for hypoglycemia 2 to 3 times daily during the initiation of the ketogenic diet, more frequently during adjustments to the ketogenic diet, and then periodically after they are stabilized on the ketogenic diet, as deemed appropriate by the patient's clinical ketogenic diet team.²⁸⁻³⁰ A rare side effect of the ketogenic diet is increased risk of kidney stone formation.²⁸⁻³⁰ Ketogenic diets, when properly followed, have not shown adverse effects on lipid profiles, but due to the higher fat content of the ketogenic diet, plasma lipid profiles should be monitored every 6 months.²⁸⁻³⁰ Some patients have experienced a transient increase in seizures during the initiation of the ketogenic diet.²⁸⁻³⁰

11.3 Use of ketogenic diet in this study. The ketogenic diet may provide benefits for patients with gangliosidoses by the following mechanisms:

- 1) Minimize or reduce the severity of food-drug interactions between miglustat and carbohydrates
- 2) Reduce seizure activity
- 3) Increase the bioavailability of miglustat to the central nervous system

11.4 Initiation and management of the ketogenic diet. The ketogenic diet must be initiated and managed by a clinical ketogenic diet team. Members of this team will include a ketogenic dietician and neurologist trained in the ketogenic diet. The ketogenic diet team will work in collaboration with the patients' doctor [name], PhD, Pediatric Geneticist and Primary Care Pediatrician; and [name], Clinical PharmD. The patients will be admitted to hospital for 2-3 days for initiation of the ketogenic diet, during which time the goal will be to transition them from their previous diet to a 1:1 ketogenic diet, and then to a 2:1 ketogenic diet. During hospitalization, urine or plasma ketones and blood glucose will be monitored per the institution's policy for ketogenic diet initiation, and the caregivers will be taught how to do home urine ketone monitoring and home blood glucose testing. The patient may be further transitioned to a 3:1 and then to a 4:1 ketogenic diet after discharge from the hospital. Ketogenic diet management will be performed not only at the University of Minnesota, but also locally by a local ketogenic diet team that works in close communication with the University of Minnesota ketogenic diet team. This teamwork relationship will be established prior to the subject beginning their transition to the ketogenic diet at the University of Minnesota. Communication between the two ketogenic diet teams will occur prior to the subject beginning

their transition to the ketogenic diet at the University of Minnesota, and will recur weekly during the period in which the child is transitioning to the ketogenic diet, as well as whenever questions arise.

The ketogenic diet can cause constipation. The ketogenic diet may also cause increased urination, and this could lead to dehydration. Subjects may experience lethargy while transitioning to the ketogenic diet. The lethargy often resolves once the patient is established on the ketogenic diet, but in some patients it may continue. A rare adverse effect of the ketogenic diet is the development of kidney stones.²⁸⁻³⁰ Anti-seizure medications that are classified as carbonic anhydrase inhibitors (e.g., acetazolamide, topiramate) have been associated with the development of kidney stones on rare occasions.³¹ Patients using anti-seizure medications that are classified as carbonic anhydrase inhibitors may be at increased risk of development of kidney stones.³¹ Ensuring adequate hydration and avoiding use of anti-seizure medications that are carbonic anhydrase inhibitors will help minimize risk of kidney stone formation.³¹

11.5 Other parameters being monitored. The following parameters will be monitored at baseline and then every 3 months for the first year of treatment, and then every 6 months thereafter: subject weight, height, occipital-frontal circumference, comprehensive metabolic panel (including serum creatinine and estimated GFR and liver function tests), CBC with platelets and differential, lipid panel, neurologic exam to assess for peripheral neuropathy, and urine pregnancy test in all post-pubertal females. It is acceptable for this interval safety monitoring to not occur at the primary study site as long as the neurologic exam could be performed by an experienced practitioner.

12.0 Study Objectives

12.1 Primary objective. The primary analysis for Syner-G treatment regimen will use the intention-to-treat (ITT) population and evaluate overall survival. This will be evaluated based on chronological age at time of death or conclusion of study (whichever occurs first), and compared to available natural history data. Median survival will be compared to previously reported natural history studies of infantile⁹ and juvenile¹¹ forms. Median survival of patients with infantile GM2 gangliosidosis was estimated at 47 months based on data from the National Tay-Sachs and Allied Diseases database for patients born after 2000.⁹ Median survival for the juvenile form was estimated at 14.5 years.¹¹

12.2 Secondary objective. Evaluate the effect of Syner-G therapy in patients with infant and juvenile gangliosidoses on changes in neurodevelopmental status, as assessed using age-equivalent scores of the Bayley Scales of Infant and Toddler Development for expressive communication, receptive communication, fine motor skills and gross motor skills; and using the Vineland Adaptive Behavior Scales.

A secondary endpoint will be the rate of change (i.e., slope) in neurocognitive functioning over the duration of follow-up, compared to available natural history data. This analysis will be conducted separately for each of the two sub-types: infantile and juvenile. The primary neurocognitive functioning endpoint for both pediatric groups is age-equivalent scores of the Bayley Scales of Infant and Toddler Development for expressive communication, receptive communication, fine motor skills and gross motor skills. Another primary neurocognitive functioning endpoint for both pediatric groups is age-equivalent scores of the Vineland Adaptive Behavior Scales. Using general estimating equations (GEE) and an exchangeable working correlation structure, variance estimation for confidence intervals and P-values will take into

account the possible correlated nature of multiple measurements on the same individual. Supportive analyses will include evaluation using the per-protocol (PP) population.

13.0 Study Design

13.1 Overview of study design. Both retrospective and prospective data will be collected during this study. This is a single-arm treatment protocol, with intention-to-treat per-protocol design. The primary analysis for Syner-G treatment regimen will use the intention-to-treat (ITT) population and evaluate overall survival. This will be evaluated based on chronological age at time of death or conclusion of study (whichever occurs first), and compared to available natural history data. This will be conducted separately for each of the two sub-types: infantile and juvenile. The neurocognitive functioning endpoint for both groups is the cognition domain of the Bayley Scales of Infant and Toddler Development for expressive communication, receptive communication, fine motor skills, gross motor skills; and the Vineland Adaptive Behavior Scales. Each of the other 4 domains will be evaluated as secondary endpoints. Using general estimating equations (GEE) and an exchangeable working correlation structure, variance estimation for confidence intervals and P-values will take into account the possible correlated nature of multiple measurements on the same individual. Supportive analyses will include evaluation using the per-protocol (PP) population.

Subgroup analyses: analyses will be repeated among GM1 gangliosidosis patients and among GM2 gangliosidosis patients, and among the infantile and juvenile forms of both GM1 and GM2 gangliosidosis.

Yearly evaluations, whenever possible, will also explore changes in seizure frequency and severity, and in movement disorders, evaluated by neurologist and parent-report.

Some subjects do not have insurance coverage for certain evaluations. Sometimes the insurance coverage changes and clinical care that was covered in the past is no longer covered. The investigators will continue to see these patients annually, whenever possible, and will provide the scheduled clinical-care visits according to what is allowed within the restrictions of the subject's health care insurance. When any given subject is unable to make their annual visit to the University of Minnesota due to illness or weakness, this will not cause them to be withdrawn from the research study. The reason for foregoing the evaluation will be documented in the subject's file, and the investigators will continue to follow them through telephone contacts with family members and health care providers.

13.2 Study population. Study population will be any patient with an infantile or late-infantile/juvenile gangliosidosis disease.

13.3 Sample size. A total of 30 infants or children:

- 5 patients with infantile Tay-Sachs disease
- 5 patients with juvenile Tay-Sachs disease
- 5 patients with infantile Sandhoff disease
- 5 patients with juvenile Sandhoff disease
- 5 patients with infantile GM1 gangliosidosis
- 5 patients with juvenile GM1 gangliosidosis

13.4 Subject recruitment. Subjects will be recruited from the investigators' clinical practice and through the Lysosomal Disease Network. This clinical trial will be posted on ClinicalTrials.gov and this may serve to recruit patients to the study.

13.5 Subject screening. Eligibility will be assessed during a baseline evaluation and will include confirmation of gangliosidosis disease via mutation analysis and tissue (e.g. leukocyte) ascertainment of level of hexosaminidase or β -galactosidase enzyme activity.

13.6 Prior and concomitant therapy. Subjects may have had previous therapies for gangliosidosis. If subjects are taking miglustat and/or pyrimethamine, and/or are on a ketogenic diet at the time of screening, they will be allowed to continue these therapies and will be allowed to participate in the Syner-G study.

13.7 Inclusion criteria. Subjects will be eligible to participate in the study if all of the following criteria are met: 1) confirmed diagnosis of infantile or juvenile GM1 or GM2 gangliosidosis via mutation analysis and tissue enzyme activity analysis (e.g. leukocyte activity of β -hexosaminidase A, including percent activity contributed from both α -subunit and β -subunits) or tissue β -galactosidase enzyme activity; 2) subjects must be age 0 - 17 years at time of enrollment; and 3) subjects and their caregivers must work closely with their University of Minnesota ketogenic diet team, and with their local ketogenic diet team, which must include a ketogenic dietician and a neurologist trained in the ketogenic diet.

13.8 Exclusion criteria. Subjects will not be eligible to participate in the study if any of the following criteria are met: 1) a desire to not participate; 2) children with severe renal impairment will be excluded from the study; 3) post-pubertal females who are pregnant or unwilling to use highly-effective methods to prevent pregnancy will be excluded from the study; 4) breast-feeding females will be excluded from this study; and 5) subjects who have an allergy to miglustat or any of the components within the drug product will be excluded from this study.

13.9 Exit/discontinuation criteria. Subjects will exit the study if any of the following conditions exist: 1) subject voluntarily withdraws from the study; 2) subject acquires any of the listed exclusion criteria; 3) subject develops severe renal impairment; 4) subject becomes pregnant; or subject's well-being, in the opinion of the Investigator, would be compromised by study continuation.

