A pharmacokinetic profile study of miglustat in healthy rats showed miglustat to be well absorbed after a single oral administration with an oral bioavailability of 40-60%. Miglustat is eliminated renally by glomerular filtration and active secretion. Hepatic clearance of miglustat was shown to be negligible. Miglustat was found to have good partitioning into most tissues evaluated, including bone marrow, lungs, heart, kidney, bladder, liver, stomach, and small and large intestine. Miglustat showed appreciable distribution into the rat brain tissue. The ratio of tissue:plasma AUC for the rat brain was 0.40. Miglustat elimination half-life in the rat plasma was approximately 5 hours, but was significantly longer in the brain tissue at 17 hours.²⁰

10.6 Miglustat elimination. The major elimination route for miglustat is renal. Miglustat is excreted unchanged in the urine.²⁶

10.7 Renal insufficiency. In adult Gaucher disease patients, initial starting dose may be reduced to 100 mg twice daily for creatinine clearance 50-70 ml/min/1.73 m²; 100 mg once daily for 30-50 ml/min/1.73 m²; and miglustat is not recommended for Gaucher patients with renal clearance less than 30 ml/min/1.73 m².²⁶

10.8 Hepatic disease. Miglustat is not metabolized and no dose adjustments are needed for hepatic function impairment.²⁶

10.9 Toxicology. The most common adverse effects of miglustat in adult Gaucher disease type I are gastrointestinal side effects of diarrhea (up to 100% of patients), flatulence (29-50% of patients), weight loss (39-67% of patients), abdominal pain (18-67% of patients), and benign intentional tremor (up to 33% of adult Gaucher disease type I patients).²⁵ The gastrointestinal side effects are due to miglustat's inhibition of the action of disaccharidase digestive enzymes in the gut, primarily maltase, sucrose, and to a lesser degree, lactase. The disaccharidase inhibition can cause side effects of osmotic diarrhea when patients eat dairy foods, starchy foods such as bread, pasta and potatoes, and foods containing a high amount of sugar.^{26,27} Overdoses in adults lead to neutropenia, which predisposes to severe infection.

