The miglustat dose will be prepared by dissolving contents of one 100 mg capsule in 10 ml of water in a medication dosing syringe. The child's parents will be taught by the study investigator how to measure the 10 ml of water and mix with miglustat powder in the syringe prior to administration. Only one dose of miglustat will be prepared at a time and the preparation must be used immediately and not stored for future use. Any unused solution during the initial dose escalation should be discarded. Parent should use a mask and gloves during preparation of miglustat solution.

10.12 Miglustat dose titration schedule.

For subjects with a BSA of < 1.3 m², the goal dose will be 100 mg three times daily.

The miglustat dose will be titrated over approximately 8 weeks to a goal dose of 100 mg 3 times daily in pediatric patients in this study, according to the following titration schedule:

The contents of one 100 mg capsule will be dissolved in 10 ml water and then 5 ml of this solution (50 mg, dissolved in 5 ml water), will be administered once daily in the evening for two weeks.

If the 50 mg once daily dose is well tolerated (i.e., patient does not show signs of gastrointestinal side effects of diarrhea, reflux or gastrointestinal cramping), then the dose will be increased to 100 mg once daily for two weeks.

The 100 mg dose will be prepared by dissolving contents of one 100 mg capsule in 10 ml of water, followed by administration of the 100 mg dose (dissolved in the 10 ml water) once daily in the evening for two weeks.

If the 100 mg once daily dose is well tolerated (i.e., patient does not show signs of gastrointestinal side effects of diarrhea, reflux or gastrointestinal cramping), then the dose will

be increased to 100 mg twice daily for two weeks. Each 100 mg dose will be prepared by mixing contents of one 100 mg capsule in 10 ml of water for each dose, and using each dose immediately after preparation (do not save any unused portion of the mixture).

If the 100 mg twice daily dose is well tolerated (i.e., patient does not show signs of gastrointestinal side effects of diarrhea, reflux or gastrointestinal cramping), then the dose will be increased to 100 mg three times daily for two weeks. Each 100 mg dose will be prepared by mixing contents of one 100 mg capsule in 10 ml of water for each dose, and using each dose immediately after preparation (do not save any unused portion of the mixture).

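### Baseline eGFR is measured but sets no miglustat dose, so, depending on what 'severe' means in 13.8, a child with stable moderate renal impairment can be titrated to the full BSA goal

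*Combined protocol and SAP*

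**What the plan says.** - **Elimination.** 10.6: "The major elimination route for miglustat is renal", and the drug is excreted unchanged. 10.8: "Miglustat is not metabolized and no dose adjustments are needed for hepatic function impairment".
- **Renal background.** For adult Gaucher patients, 10.7 reports that the "initial starting dose may be reduced to 100 mg twice daily for creatinine clearance 50-70 ml/min/1.73 m²". It gives 100 mg once daily for 30-50 and adds that "miglustat is not recommended for Gaucher patients with renal clearance less than 30 ml/min/1.73 m²".
- **Study dose.** 10.10 sets the goal by body surface area: 100 mg three times daily, or the most the child tolerates up to that, and up to 200 mg three times daily above 1.3 m². 10.12 starts at 50 mg once daily and moves up every two weeks if the "patient does not show signs of gastrointestinal side effects of diarrhea, reflux or gastrointestinal cramping". Above 1.3 m², insurance cover also limits the dose. 10.13 adjusts for neuropathy, low platelets and gastrointestinal effects.
- **Entry.** 13.8: "children with severe renal impairment will be excluded from the study". The Synopsis says the same, and neither gives a value. Under 13.5, eligibility is judged at a baseline evaluation.
- **Monitoring and exit.** 11.5 and 15.1 schedule creatinine, eGFR and CBC with differential at baseline, every 3 months in year 1, then every 6 months. 13.9 removes a child who develops severe renal impairment. 21.2 withdraws a child who develops kidney function problems on study, again without a value.

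**The concern.** The protocol recognises that clearance depends on the kidney and measures kidney function before treatment, but does not connect that measurement to the dose. The only test between one titration step and the next is gastrointestinal. 10.9 attributes those effects to miglustat's "inhibition of the action of disaccharidase digestive enzymes in the gut", and 20.2 expects the ketogenic diet to reduce them. By inference, passing the test says little about whether the drug is accumulating systemically.

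What is at stake is higher systemic exposure in a child whose reduced clearance was known at entry. 10.9 states: "Overdoses in adults lead to neutropenia, which predisposes to severe infection". It also lists peripheral neuropathy as a known risk and thrombocytopenia as a known side effect. 10.13 has steps for those two but none for neutropenia.

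The entry and exit rules also sit awkwardly together. A child whose eGFR falls to 45 on study could be withdrawn under 21.2, while a child who enters with a stable 45 could be titrated to the full goal.

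**Working it through.** The plan states no figure on this point, so there is nothing to reproduce. The check has four steps.

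**1. Which rule acts on a child entering with stable eGFR of 30 to 70?**

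| Rule | Acts on this child? |
|---|---|
| 13.8 exclusion | Only if 'severe' is set above the child's eGFR |
| 10.10-10.12 goal and titration | No renal term |
| 10.13 adjustments | Only after neuropathy, low platelets or gastrointestinal effects |
| 13.9 renal exit, 21.2 withdrawal | Only for impairment that develops on study |
| 13.9 well-being clause | At the investigator's discretion |
| 19.1 dose reduction | After an adverse effect, if indicated |

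None sets the dose in advance from the baseline eGFR.

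**2. Expected exposure at the same dose.** Relative steady-state exposure is R = 1 / (1 − fe × (1 − CL/N)). Here fe is the renal fraction of elimination, CL the child's clearance and N normal clearance, both in ml/min/1.73 m². The values of CL are the band edges in 10.7. fe = 1 follows 10.6 and 10.8. N = 100, linear kinetics, proportionality to clearance, and reading eGFR as creatinine clearance are assumptions.

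| | CL 70 | CL 50 | CL 30 |
|---|---|---|---|
| fe = 1, N = 100 (central) | 1/0.70 = 1.43 | 1/0.50 = 2.00 | 1/0.30 = 3.33 |
| fe = 0.8, N = 90 (lowest) | 1.22 | 1.55 | 2.14 |
| fe = 1, N = 120 (highest) | 1.71 | 2.40 | 4.00 |

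**3. Effect of a cap.** Exposure relative to normal is (cap/goal) × R, under the central assumptions.

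- Two-thirds of goal at 50 to 70: 2/3 × 1.43 = 0.95, to 2/3 × 2.00 = 1.33.
- One-third of goal at 30 to <50: 1/3 × 2.00 = 0.67, to 1/3 × 3.33 = 1.11.
- In mg/day this is 200 and 100 for a 300 mg goal, and 400 and 200 for a 600 mg goal.
- Applying the 10.7 doses unchanged to a 600 mg goal gives 200/600 × 1.43 to 2.00 = 0.48 to 0.67, and 100/600 × 2.00 to 3.33 = 0.33 to 0.56. That is too low, so the cap should scale with the goal.

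**4. When the later safeguards act.** With no delays, 10.12 reaches 300 mg/day after 3 × 2 = 6 weeks of miglustat (50, 100, then 200 mg/day). It reaches 600 mg/day after 6 × 2 = 12 weeks (adding 300, 400 and 500 mg/day). The first scheduled panel after baseline is at month 3. Calls are at least weekly during titration (17.0), but a call cannot detect a falling neutrophil or platelet count.

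**The case against.** The strongest reply has five parts.

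- **The gap depends on an undefined word.** This stands. If 'severe' were set well above 30, much or all of the 30 to 70 range would be excluded. The goal is also a ceiling, reached only if tolerated.
- **Renal review already exists.** 13.5 and 15.1 imply that eGFR is seen before a new starter's first dose, and 10.11 delays miglustat until two stable weeks on the diet. This also stands. What is missing is a dose action, not the measurement.
- **Monitoring limits the harm.** The start is low, CBC with differential is scheduled, and 19.1 allows dose reduction for any adverse effect. These do limit harm, but they work after exposure has risen.
- **Harm is not shown.** A reader might infer that these children would be overdosed to the point of neutropenia. The sentence in 10.9 concerns adult overdoses and gives no dose or exposure, so nothing places a 1.4- to 3.3-fold ratio at that level. Rat data in 5.1 and 10.5 also report active secretion, so exact proportionality to creatinine clearance is not established. The ranges in the working do not test that.
- **10.7 is not a paediatric rule.** A reader might infer that the trial breaches 10.7, since 300 mg/day exceeds the doses listed there. It does not. 10.7 is adult, permissive and about starting doses, and the trial's 50 mg once-daily start is below both reduced doses.

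Nothing in the documents suggests that renal impairment is common in these diseases.

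**Conclusion.** The point holds conditionally. If 'severe' means roughly <30 ml/min/1.73 m², a child with stable eGFR of 30 to 70 at entry is eligible. Subject to gastrointestinal tolerance, the written rule takes that child to the full BSA goal. Expected exposure is about 1.4, 2.0 and 3.3 times normal at 70, 50 and 30. Varying the assumptions gives 1.2-1.7, 1.6-2.4 and 2.1-4.0. The documents contain no paediatric exposure data in renal impairment.

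The flat reading, that every moderately impaired child will receive the full dose, is not supported: it depends on the cut-off, on tolerance and on investigator discretion. Few if any of 30 children are likely to be affected. This is a minor to moderate safety improvement, worth making because the needed measurement is already collected.

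**What to change.** 1. **In 10.12, cap the titration goal by baseline eGFR, in proportion to the BSA goal.** Use about two-thirds at 50 to 70 and one-third at 30 to <50: 200 and 100 mg/day for a 300 mg goal, 400 and 200 mg/day for a 600 mg goal. Each cap is an existing titration step, so the child simply stops there.
2. **Apply the cap to children already on miglustat at entry (13.6).** 17.0 starts the schedule of children already on the combination at a later time-point, so the text should require an eGFR at entry for them.
3. **In 13.8 and the Synopsis, state the eGFR that counts as severe, for example <30, and align 13.9 and 21.2 with it.**

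The sponsor's clinicians should confirm the values for children: the 10.7 bands are adult and 13.7 admits from age 0. They should also look at the step at 50, where expected exposure under the caps drops from 1.33 to 0.67 of normal. I would not exclude eGFR 30 to 70 outright, nor use the fixed 10.7 doses as caps for a 600 mg goal.

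The cost is mainly wording, since eGFR is already in the baseline panel. The downside is a lower dose for a very few children. A capped child need not leave the per-protocol set, because 18.1 counts compliance against prescribed doses.
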